10.2.5. Reporting of SAEs

TESAE Reporting to the Sponsor or Designee via an Electronic Data Collection Tool

- The primary mechanism for reporting an TESAE to the Sponsor or designee will be the electronic data collection tool.
- The Site will enter the TESAE data into the electronic system as soon as it becomes available.
- After the study is completed at a given Site, the electronic data collection tool will be taken off-line to prevent the entry of new data or changes to existing data.
- If a Site receives a report of a new TESAE from a study Participant or receives updated
 data on a previously reported TESAE after the electronic data collection tool has been
 taken off-line, then the Site can report this information or to the Medical Monitor or
 TESAE coordinator by telephone.

Version 1.0 65 Final: 11 Feb 2021

10.3. Appendix 3. Prohibited Medications and Procedures

Table 2 Prohibited Medications – Steroids

Drug	Example of Common Name(s)	Maximum Dose Allowed During Study
Steroids		
Injected or oral corticosteroids ^a	prednisone, betamethasone, dexamethasone, cortisone, hydrocortisone, triamcinolone	None
Topical corticosteroids on the lower legs or feet	prednisone, betamethasone, dexamethasone, cortisone, hydrocortisone, triamcinolone	None on the lower legs or feet ^b

^a Inhaled, ocular, and intra-articular steroids are allowed.

Table 3 Prohibited Medications and Procedures – Opioids and Other Therapies

Drug or Procedure	Maximum Dose Allowed During Study
Acupuncture	None
Anesthetic creams (for use only during injections) and patches, including capsaicin, on lower legs and feet	None
Benzodiazepines	None, except for stable bedtime dose
Gabapentin, pregabalin	None
Isosorbide dinitrate spray on lower legs and feet	None
Opioids (e.g., morphine, oxycodone, tramadol, methadone, fentanyl)	None, except after trauma or surgery
Skeletal muscle relaxants (e.g., cyclobenzaprine, metaxalone, chlorzoxazone)	None
Transcutaneous electrical nerve stimulation	None

Version 1.0 66 Final: 11 Feb 2021

^b Topical corticosteroid use is allowed on body surfaces other than the lower legs and feet.

10.4. Appendix 4. Abbreviations and Definitions

10.4.1. Abbreviations

Abbreviation	Definition
ADPS	Average Daily Pain Score
AE	adverse event
AESI	adverse event of special interest
ALS	amyotrophic lateral sclerosis
ALT	alanine transaminase (SGPT)
APR	Accurate Pain Reporting
AST	aspartate transaminase (SGOT)
β-HCG	Beta human chorionic gonadotropin
BMI	body mass index
BP	blood pressure
BPI-DPN	Brief Pain Inventory for Diabetic Peripheral Neuropathy
BUN	blood urea nitrogen
BST	Bedside Sensory Testing
CABG	coronary artery bypass grafting
cDNA	complementary DNA
CDRC	Clinical Data Review Committee
CFR	Code of Federal Regulations
CKD-EPI	chronic kidney disease epidemiology collaboration
CLI	critical limb ischemia
CRF	case report form
CRO	clinical research organization
CS	clinically significant
CT	Computed Tomography
DIP	distal interphalangeal
DKA	diabetic ketoacidosis
DM	diabetes mellitus
DMC	Data Monitoring Committee
DNA	deoxyribonucleic acid
DPN	diabetic peripheral neuropathy
DSMB	Data Safety Monitoring Board

Version 1.0 67 Final: 11 Feb 2021

Abbreviation	Definition
ECG	electrocardiogram
eCRF	electronic case report form
EDC	electronic data capture system
eDiary	electronic diary
eGFR	estimated glomerular filtration rate
EQ-5D	EuroQol Health Utilities Index
FDA	Food and Drug Administration
GCP	Good Clinical Practice
GGT	Gamma-glutamyl transpeptidase
GLP	Good Laboratory Practice
HbA1c	Hemoglobin A1c
HDL-C	high-density lipoprotein cholesterol
HEENT	head, eyes, ears, nose, and throat
HGF	hepatocyte growth factor
HIPAA	Health Insurance Portability and Accountability Act
IB	Investigator's Brochure
ICF	informed consent form
ICH	International Council for Harmonisation of Technical Requirements for Pharmaceuticals for Human Use
IHD	ischemic heart disease
IM	intramuscular
IND	Investigational New Drug application
IRB	Institutional Review Board
ISDN	isosorbide dinitrate
ITT	intent-to-treat
IUD	intrauterine device
IWRS	Interactive Web Response System
LDL-C	low-density lipoprotein cholesterol
mITT	modified intent-to-treat
MNSI	Michigan Neuropathy Screening Instrument
NCS	not clinically significant
NHU	nonhealing foot ulcer
NIH	National Institutes of Health
NRS	Numerical Rating Scale

Version 1.0 68 Final: 11 Feb 2021

Abbreviation	Definition
OSP	Office of Science Policy
PAD	peripheral arterial disease
PCR	polymerase chain reaction
PCP	phencyclidine
PE	physical examination
PGIC	Patient Global Impression of Change
PHI	protected health information
PI	Principal Investigator
PKC	Protein kinase C
PP	per protocol
PRR	Placebo Response Reduction
QC	quality control
QoL	Quality of Life
ROS	reactive oxygen species
SAP	statistical analysis plan
SF-36	36-Item Short Form Health Survey
SoA	Schedule of Activities
SOP	standard operating procedure
SSRI	selective serotonin reuptake inhibitor
SUSAR	suspected unexpected serious adverse reaction
TCA	tricyclic antidepressants
TEAE	treatment-emergent adverse event
TESAE	treatment-emergent serious adverse event
TENS	transcutaneous electrical nerve stimulation
THC	cannabinoid
VAS	Visual Analog Scale
VEGF	vascular endothelial growth factor

Version 1.0 69 Final: 11 Feb 2021

10.4.2. Definitions

Active Infection Chronic infection or severe active infection that may compromise the Participant's well-being or participation in the study, in the Investigator's judgment Average Daily Pain Score The mean of at least 5 daily pain scores recorded for Question 5 of the BPI-DPN (Section 10.5) in eDiary during the 7 days prior to the Visits on (ADPS) Days 270 and 365/ET Worst Daily Pain Score The mean of at least 5 worst daily pain scores recorded for Ouestion 3 of the BPI-DPN (Section 10.5) in eDiary during the 7 days prior to the Visits on Days 270 and 365/ET Day 14, etc. Day 14 (for example) refers specifically to the actual day of the Visit designated as the Day 14 Visit, and not to the 14th day of the study for a Participant. Drug Abuse The habitual taking of addictive or illegal drugs Drugs of Abuse Amphetamines, barbiturates, benzodiazepines, buprenorphine, cocaine, fentanyl, meperidine, methadone, opiates, oxycodone, oxymorphone, phencyclidine, and tramadol EMLA Cream A mixture of lidocaine 2.5% and prilocaine 2.5% First-degree relative Parent, sibling, or child Highly Effective Contraception See Section 8.4.8 Method Investigator The PI or appropriate Study Site personnel whom the PI designates to perform a certain duty The part of the leg between the knee joint and the ankle joint. Does not Lower Leg include the foot. Medical Monitor The Responsible Medical Officer or designee **Participant** An individual who has signed informed consent to be entered into the study Placebo Placebo comprises 45 mg sodium chloride and 55 mg sucrose in 5 mL of water for injection. Engensis vials contain the same excipients. Safety Analysis Population All Participants who receive a Study Injection Site A clinical research facility participating in the VMDN-003-2b study Helixmith Co., Ltd. and its representatives contracted to provide services for Sponsor study conduct ≤ 50% change in total daily dose relative to dosing at baseline of Stable Dosing Regimen any medication Stage 4 or 5 Kidney Disease eGFR < 30 mL/min/1.73 m² Study Drug Engensis or Placebo

Version 1.0 70 Final: 11 Feb 2021

10.5. Appendix 5. Brief Pain Inventory for Participants with Diabetic Peripheral Neuropathy (BPI-DPN)

The paper version of the BPI-DPN Short Form is shown below. Participants will be using an ePRO version, which will be developed prior to study startup.

		E	Brief	Pain	Inve	ntor	y (Sh	ort F	orm) - DI	PN
Da		_/	/								Time:
Na	me:		Last				Firs				iddle Initial

	D. 0 Does Interfe	1 not	al Worl 2	k (inclu 3	udes bo	th work 5	outside 6	the ho	me an 8	d hou	10 Completely Interferes	
	0 Does Interfe	1 not	ons wi	th othe 3	er people 4	5 5	6	7	8	9	10 Completely Interferes	
	F. 0 Does Interfe	100	2	3	4	5	6	7	8	9	10 Completely Interferes	
	G. 0 Does Interfe	1 not	ment o 2	f life 3	4	5	6	7	8	9	10 Completely Interferes	

10.6. Appendix 6. Patient Global Impression of Change

Patient Global Impression of Change (PGIC) Scale

Since the start of the study, my overall status is: Check (\checkmark) one box only:

Very Much Improved	1	
Much Improved	2	
Minimally Improved	3	
No Change	4	
Minimally Worse	5	
Much Worse	6	
Very Much Worse	7	

Version 1.0 73 Final: 11 Feb 2021

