Participants will be enrolled in the VMDN-003-2b study at completion of the Day 180 Visit of Study VMDN-003-2. Participants will continue to be identified by the same Participant number and the same treatment group (Engensis or Placebo) assigned by randomization in Study VMDN-003-2. No study drug or treatment will be administered in this VMDN-003-2b extension study. The double-blind treatment assignment from the prior study will be maintained for Investigators and Participants during this extension study.

Assessments to be conducted during this VMDN-003-2b extension study are as follows: vital signs, weight, BMI, physical examination, retinal fundoscopy (by an ophthalmologist), 12-lead electrocardiogram (ECG), laboratory assessments, HBA1c levels, concomitant medications and procedures, urine drug analysis, urine pregnancy test for females of childbearing potential, Accurate Pain Reporting (APR), Placebo Response Reduction (PRR), the Michigan Neuropathy Screening Instrument (MNSI), partial and full BPI-DPN, BST, and quality of life instruments (36-item Short Form Health Survey [SF-36] and EuroQol Health Utilities Index [EQ-5D]).

Assessments of TEAEs, TESAEs, AESIs, and clinically significant laboratory values will start as of the Day 180 Visit of Study VMDN-003-2 and continue throughout the VMDN-003-2b extension study through Day 365/ET.

During the last 7 days prior to the Day 270 and Day 365/ET Visits, Participants must complete the full BPI-DPN on an ePRO for determining the ADPS for at least 5 out of the last 7 days.

Follow-up Study Visits will be conducted on Days 270, 300, and 365/ET. At the Day 365/ET Visit (end of study), the following assessments will be conducted: the full BPI-DPN (performed during the 7 days prior to the Visit), MNSI, BST, Patient Global Impression of Change (PGIC), SF-36 and EQ-5D quality of life assessments, urine drug analysis, retinal fundoscopy, physical examination, concomitant medications and procedures, TEAEs, and AESIs. Blood will be drawn for determination of serum chemistry, lipid profile, pregnancy status, hematology, and HbA1c levels.

Version 1.0 11 Final: 11 Feb 2021

Study and Treatment Duration:

The timing for visits in the VMDN-003-2b study starts at the conclusion of the Day 180 Visit in Study VMDN-003-2. Participants in Study VMDN-003-2b will be followed from the Day 180 Visit (VMDN-003-2) to Day 365/ET. The VMDN-003-2b study duration is 6 months.

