No study drug or treatment will be administered in Study VMDN-003-2b.

Visit Frequency:

There will be 3 visits to the Clinical Site during the extension study (after the Day 180 Visit from Study VMDN-003-2) on Days 270, 300, and 365/ET.

Intervention Groups and Duration:

Two treatment groups of Participants (Engensis or Placebo) from Study VMDN-003-2 will be followed in a double-blind fashion from Day 180 Visit (Study VMDN-003-2) through Day 365/ET of this extension protocol. No study drug (Engensis or Placebo) will be administered in the VMDN-003-2b study.

Number of Participants:

[figure not shown]
The number of Participants to be enrolled in this 6-month extension study depends upon the number of subjects who complete the Day 180 Visit in Study VMDN-003-2 and provide written informed consent for this extension protocol (prior to or during their Day 180 Visit in the VMDN-003-2 study).

Data Safety Monitoring Board:

The independent Data Safety Monitoring Board (DSMB) will periodically review a limited set of unblinded (noncomparative) tables and/or listings, including all reported TEAEs, TESAEs, and AESIs.

Version 1.0 12 Final: 11 Feb 2021

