- 7. Urine Drug Analysis includes amphetamines (methamphetamine), barbiturates, benzodiazepines, buprenorphine, cannabinoid (THC), cocaine, oxycodone, methadone, opiates, phencyclidine (PCP), tricyclics (TCA), and ethyl alcohol. Cannabinoid detection is not an exclusion criterion but may be used in exploratory analyses. The urine drug analyses will be conducted on Days 270, 300, and 365/ET. Drug analyses will be performed by the central laboratory.
- **8. HbA1c** levels will be measured on Day 365/ET.
- 9. Concomitant Medications and Procedures: All medications or vaccines, including over-the-counter or prescription medicines, vitamins, herbal supplements, and procedures that the Participant receives will be recorded on Days 270, 300, and 365/ET. For each medication, treatment, or procedure, the following information will be collected: Medication trade or generic name or type of procedure, indication, start date, stop date or ongoing, dose, units, frequency, and route.
- Accurate Pain Reporting (APR): The Accurate Pain Reporting training will be conducted on Days 270, 300, and 365/ET.
 - **Placebo Response Reduction (PRR):** The Placebo Response Reduction training will be conducted on Days 270, 300, and 365/ET.
- 11. Brief Pain Inventory (BPI-DPN) Full Questionnaire will be administered through the ePRO daily starting at 7 days prior to Day 270 and Day 365/ET. The mean of the Average Daily Pain Scores (ADPSs, used for the primary endpoint) is the mean from a minimum of 5 ADPSs recorded in the 7 days prior to the Days 270 and 365/ET Visits. If the ePRO contains fewer than 5 daily entries over the 7 days prior to the Day 270 and Day 365/ET Visits, the visit must be rescheduled (up to 3 days later) so that the Participant can record 5 daily entries over the 7 days.
- **12. Brief Pain Inventory (BPI) Partial Questionnaire** (questions 3, 5, and 9a from the full questionnaire) will be completed on the ePRO every day that the full BPI is *not* conducted from the Day 180 Visit (VMDN-003-2, Initial Visit for this extension study) to the Day 365/ET Visit.

Version 1.0 15 Final: 11 Feb 2021

- 13. Quality of Life Questionnaires (SF-36, EQ-5D) will be administered on Day 270 and Day 365/ET. The study coordinator will check the questionnaires for completeness. Any omissions or ambiguous answers will be clarified by the Participant prior to leaving the clinic.
- 14. Patient Global Impression of Change (PGIC) will be administered on Days 270 and 365/ET.

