5. STUDY POPULATION

Participants for this 6-month extension study will come from the main study (Study VMDN-003-2) in which Participants complete the Day 180 Visit and give signed informed consent for the extension study.

The number of Participants who meet these qualifications will determine the number of Participants for this extension study.

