8.2.2. Quality of Life/Participant Reported Outcome Measures

8.2.2.1. Patient Global Impression of Change

The Participant's impression of change after treatment will be measured with the Patient Global Impression of Change (PGIC) questionnaire through use of an eDiary. The Investigator should ensure that the Participant is provided with instructions and is trained to use the eDiary and to complete the assessment tool properly before data collection begins (Section 10.6, Appendix 6). This questionnaire measures the Participant's perception of how treatment has affected their level of activity, symptoms, emotions, and overall quality of life. Each descriptor is ranked on an intensity scale of 1 = Very Much Improved; 2 = Much Improved; 3 = Minimally Improved; 4 = No Change; 5 = Minimally Worse; 6 = Much Worse; 7 = Very Much Worse. The test will be self-administered during the Day 270 and Day 365/ET Visits.

Upon completion of the questionnaire, the study coordinator will check the questionnaire for completeness. Any omissions or ambiguous answers will be clarified by the Participant prior to leaving the clinic.

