9.2. Populations for Analyses

9.2.1. Intent-To-Treat Population

This subset includes all enrolled Participants in this study who start this extension study at the Day 180 Visit (Study VMDN-003-2). Participants in the ITT population will be analyzed according to original treatment assignment in Study VMDN-003-2, regardless of actual treatment received. The primary analyses of the primary and secondary efficacy endpoints will be based on this ITT population.

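### The PGIC item at Days 270 and 365 does not say which study's start it refers to, so a benefit gained by Day 180 and then held can be rated as improvement or as no change

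*Protocol*

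**What the plan says.** **The item.** Protocol Appendix 6 (section 10.6) holds the only PGIC wording in the documents. It reads "Since the start of the study, my overall status is", followed by a seven-point scale from Very Much Improved (1) through No Change (4) to Very Much Worse (7). The Schedule of Activities and section 8.2.2.1 place it at Day 270 and Day 365/ET.

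**When this study starts.** The synopsis says: "The timing for visits in the VMDN-003-2b study starts at the conclusion of the Day 180 Visit in Study VMDN-003-2". Footnote 12 of the Schedule of Activities calls the Day 180 Visit the "Initial Visit for this extension study". Section 9.2.1 defines the ITT population by participants starting the extension at that visit. Section 5 requires that they "give signed informed consent for the extension study".

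**What the PGIC is meant to measure.** Section 8.2.2.1 says: "The Participant's impression of change after treatment will be measured with the Patient Global Impression of Change (PGIC) questionnaire". By the synopsis, the injections were given on Days 0, 14, 90 and 104 of the main study, and "No study drug or treatment will be administered in Study VMDN-003-2b". SAP section 10.2 sets the default baseline at or before the start of dosing in VMDN-003-2.

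**How the endpoint is listed.** Protocol section 9.3.3 lists PGIC at Days 270 and 365 as exploratory, with no reference point. SAP section 12.5.2.3 says only that it is summarized by treatment group.

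**The concern.** A global impression of change means little unless respondent and analyst share the same starting point. Here the words on the form, read with this protocol's usual account of when the extension begins, point to Day 180. The stated purpose of the measure points to Day 0.

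The two readings diverge most for the participants a durability study cares about. Someone who improved before Day 180 and kept the gain is better than at Day 0 and unchanged since Day 180. Someone who kept most of the gain could even report slight worsening since Day 180. At stake is whether the Day 270 and Day 365 ratings can be read as evidence of sustained benefit. Section 4.3 of the protocol relies on the PGIC as a validated tool for response in the sense of clinical benefit. Once the ratings are collected, no analysis rule can recover which anchor a participant used.

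**Working it through.** The documents give no PGIC rate, sample size or power to reproduce, so the check is a comparison of passages followed by a labelled illustration.

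**Step 1: does any visible text fix the anchor?**

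| Place | What it implies for the PGIC reference |
|---|---|
| Appendix 6, item wording | Start of an unnamed study |
| Synopsis; Schedule of Activities footnote 12; section 9.2.1 | This study starts at Day 180 |
| Section 8.2.2.1 | Change after treatment, hence Day 0 |
| Schedule of Activities, study-day footnote | Days are counted from main-study Day 0 |
| Section 3 and synopsis | Days 0, 104 and 180 all serve as reference points |
| Section 9.3.3 | Day 0 named for changes in BST, ADPS, severity scores, MNSI, SF-36 and EQ-5D; Day 180 for rescue medication; none for PGIC |
| Section 10.4.2, definitions | The start of the study is not defined |
| SAP 10.2 | Default baseline is before main-study dosing, but PGIC has no baseline value for this to act on |
| SAP 12.5.2.3 | Summary by arm, no anchor |

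No visible passage settles it. The reference cannot be inferred from the endpoint list either, because that list uses both Day 0 and Day 180 for other measures.

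**Step 2: one participant.** Suppose status improves clearly by Day 180 and is the same at Day 365. Against Day 0 a fair answer is Much Improved (2). Against Day 180 a fair answer is No Change (4). The same course gives ratings two steps apart.

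**Step 3: the between-arm difference.** Let p1 and p2 be the proportions rated improved on Engensis and Placebo when everyone anchors at Day 0. Let q be the share anchoring at Day 180, equal in both arms. Let c be the improved proportion among those who anchor at Day 180, also equal in both arms because the effect is held. Then:

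- observed rate in arm i = (1 − q) × p_i + q × c
- observed difference = (1 − q) × (p1 − p2), because the term q × c cancels

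The rates and q below are assumptions; none comes from the documents.

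| q | Assumed 50% vs 35% (15 points) | Assumed 40% vs 30% (10 points) |
|---|---|---|
| 10% | 0.90 × 15 = 13.5 | 0.90 × 10 = 9 |
| 25% | 0.75 × 15 = 11.25, about 11.3 | 0.75 × 10 = 7.5 |
| 50% | 0.50 × 15 = 7.5 | 0.50 × 10 = 5 |
| 100% | 0 | 0 |

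The value of c does not matter. At q = 50% with 50% vs 35%, c = 0% gives 25% vs 17.5%, and c = 10% gives 30% vs 22.5%. Both differ by 7.5 points.

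**The case against.** The best answer is that participants will mostly think of Day 0. They keep the same number and treatment arm, visits are numbered from main-study Day 0, the synopsis describes a combined 12 months, and section 9.2.3 speaks of a 12-month follow-up. The definition of visit days in section 10.4.2 also uses the word study on the Day 0 clock. Nothing is injected at Day 180 that would mark a new beginning. Section 8.2.2.1 requires instruction and training on completing the tool, and has ambiguous answers clarified before the participant leaves. The eDiary screen and training script are not in these documents and may be clearer.

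Much of this stands. It makes the Day 0 reading plausible for many participants and a small q possible. It does not close the gap, because the visible training requirement fixes no anchor and a coordinator cannot see an ambiguity behind a cleanly ticked box.

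A reader might infer four stronger things that the documents do not support:

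- That the ratings do mix two reference points. The wording makes this possible; nothing shows how many participants use each.
- That the same response gets opposite scores. Much Improved and No Change differ by two steps; they are not a reversal.
- That the wording biases the comparison towards one arm. Both blinded arms see the same item, so with a held effect the expected consequence is dilution.
- That a planned comparison with main-study PGIC, or a planned use of PGIC to interpret the pain change, is lost. No visible text plans either, and the main-study form is not available here.

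It is also fair that PGIC is exploratory and, in the visible SAP, only summarized. Redacted SAP text may add analysis detail, but could not restore a reference point that was never recorded.

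**Conclusion.** The point holds as an ambiguity in the recall anchor, worth correcting but limited in reach. Used exactly as printed, the form can record a benefit gained by Day 180 and held as No Change, in a study whose purpose is durability. The size is the factor (1 − q). It rests on a held effect, the same q in both arms, and equal Day 180-anchored ratings across arms. Because q is unknown, the loss could be trivial (1 to 1.5 points at q = 10% in the two assumed scenarios) or complete at q = 100%. The primary ADPS endpoint and the secondary worst-pain and responder endpoints do not use this item and are unaffected.

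**What to change.** State the reference in the ePRO item as the time just before the first study injection, Day 0 of VMDN-003-2. For example: *Compared with just before your first study injection (Day 0 of VMDN-003-2), my overall status is*. If the item must stay identical to the main-study form, leave it unchanged and put the same reference in a fixed instruction shown with it and in the site script. Give that reference in Protocol sections 8.2.2.1 and 9.3.3 and in the SAP.

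The cost is one line of ePRO text or instruction, with matching edits to the protocol, SAP and site materials. The response scale does not change. The downside of rewording the item is a small difference from any main-study PGIC form; the fixed-instruction route leaves the item itself untouched. If ratings have already been collected with the printed wording, report the ambiguity as a limitation.
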